6.13 SAFETY ANALYSES

Safety analyses will be based on the Safety population consisting of all subjects receiving any amount of somavaratan or rhGH.

6.13.1 Adverse Events

Analysis of adverse events will be based on Treatment Emergent events. A Treatment Emergent Adverse Event (TEAE) is any sign, symptom, or abnormal laboratory finding after the first drug administration, or an increase in the severity or frequency of a condition existing at the time of enrollment. Procedures will not be included as an adverse event, but any condition not present at enrollment, or change in condition, leading to the procedure should be classified as an adverse event.

AEs will be reported by the Investigator and coded using the MedDRA dictionary. AE severity will be determined using the CTCAE v4.0 definitions. Severity of AEs that are not classified using CTCAE will be assigned scores based on the following:

Severity of Adverse Events

Grade 1	Mild	Asymptomatic or mild symptoms; clinical or diagnostic observations only; intervention not indicated.
Grade 2	Moderate	Minimal, local, or noninvasive intervention indicated; limiting age-appropriate instrumental activities of daily living. ¹
Grade 3	Severe	Severe or medically significant but not immediately life-threatening; hospitalization or prolongation of hospitalization indicated; disabling; limited self-care activities of daily living. ²
Grade 4	Life-threatening	Life-threatening consequences; urgent intervention indicated.
Grade 5	Death	Death related to the AE.

¹ Examples of instrumental activities of daily living include: Watching television, using a computer, playing video games, attending school, playing outside, using the telephone, etc.

² Examples of self-care activities of daily living are: bathing, dressing and undressing, feeding self, using the toilet, taking medications, etc.

For analysis purposes, all AEs will be classified to the appropriate MedDRA preferred term (PT) and system organ class. For each subject, multiple events that map to the same PT will only be counted once for the PT, and multiple PTs within a System Organ Class (SOC) will only be counted as one occurrence for that SOC to assess subject incidence of events. The count and percentage of subjects with each PT and SOC will be summarized for each treatment group.

Relationship and severity of adverse events will be summarized (subject count, % of subjects) for each treatment group. For these summaries, multiple occurrences of an event within a subject will be classified as a single observation with the strongest relationship and maximum severity ratings. In addition, frequency tables of all reported events with each associated relationship and severity will be presented.

A tabulation of the incidence of all Grade 3 and 4 treatment-emergent adverse events will be displayed, overall and those related to study drug. Furthermore, a tabulation of the incidence of all treatment-emergent injection site adverse events will be created including, but not limited to, events such as pain/tenderness, erythema, lipoatrophy, stinging, burning, itching, etc. A listing of the treatment-emergent injection site adverse events will supplement the tabulation and will contain dosing information including but not limited to, onset time since last dose, relationship to study drug, dose, grade, injection location, injection volume, number of injections received per dosing event, and duration.

Moreover, a listing of instances of headache reported as an adverse event will be presented which will include information about the event such as, but not limited to, onset time since last dose, relationship to study drug, dose, grade, and duration.

Serious Adverse Events (SAE) are defined as those events that are life threatening, require hospitalization or prolong existing hospitalization; or cause disability, incapacity, or death; or require intervention to prevent such outcomes. These events will be classified as SAEs by the Investigator and appropriate medical review and will be summarized by treatment group, as well as total subjects exposed.

A listing of SAE data will be provided to supplement the tabulated results.

6.13.2 Physical Exams

For the complete physical examinations performed, the proportion of subjects reporting results of “Normal”, “Abnormal, Not Clinically Significant,” and “Abnormal, Clinically Significant” will be calculated and presented for each scheduled time point, body system and treatment group. Any changes in physical examinations post-injection, including injection site findings, will be captured as an AE and will be presented in those tabulations and/or listings. The proportion of subjects that report changes in brief physical examination (e.g., change/no change) will be calculated and presented by treatment group across visits.

6.13.3 Vital Signs and ECG

Descriptive statistics of vital signs will be calculated at each scheduled time point and will include the raw change from Baseline. The summary of descriptive statistics at each time point will be displayed by treatment group.

A listing of all vital signs data will be provided to supplement the tabulated results.

ECG abnormalities from Screening and Month 3 will be listed. A count and percent of subjects with abnormal changes (normal at screening, abnormal findings at Month 3) will be presented.

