4.2 Inclusion Criteria

Each subject must meet the following criteria to be enrolled in this study.

1. Chronological Age \geq 3.0 years and \leq 10.0 (girls) and \leq 11.0 (boys).
2. Pre-pubertal status: Absent breast development in girls, testicular volume $<$ 4.0 mL in boys.
3. Diagnosis of GHD as documented by two or more GH stimulation test results \leq 10.0 ng/mL. The use of prior GH stimulation test results is permitted providing the stimulatory agents, GH assay and test results are approved in writing by the medical monitor.
4. Height SD score \leq -2.0 at screening.
5. Weight for Stature \geq 10th percentile.
6. IGF-I SD score \leq -1.0 at screening.
7. Delayed bone age (\geq 6 months as determined by the central reader). Left hand X-Ray must be obtained within 90 days of screening visit or during screening.
8. Normal thyroid function test results at screening visit (or a minimum of four weeks of thyroxine replacement therapy prior to study drug administration).
9. Available adrenal function test results at screening visit (or in the preceding 6 months) in all subjects without a minimum of four weeks glucocorticoid replacement therapy prior to study drug administration. The following interpretive guidelines will be used:

Morning cortisol (06:00-09:00 hr):

- Normal $>$ 10.0 μ g/dL
- Intermediate 6.0-9.99 μ g/dL
- Low $<$ 6.0 μ g/dL **or**

ACTH, Glucagon, Insulin or other Stimulation test:

- Normal $>$ 20.0 μ g/dL

- Intermediate 15.0-19.9 $\mu\text{g}/\text{dL}$
- Low $< 15.0 \mu\text{g}/\text{dL}$

Subjects with low cortisol values must receive glucocorticoid treatment for a minimum of 4 weeks before study drug administration. Subjects with intermediate cortisol values should receive temporary stress doses of glucocorticoid at the discretion of the Investigator.

10. Pathology relating to cause of GH deficiency must be stable for at least 6 months prior to screening.
11. Legally authorized representatives must be willing and able to give informed consent.

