Possibly	An AE that follows a reasonable temporal sequence from study drug administration, AND follows a known response pattern to the use of the study drug, BUT could have been produced by the subject's clinical state including concurrent disease or other modes of therapy administered to the subject.
Unlikely	An AE occurring after study drug exposure whose relationship to study drug cannot be entirely ruled out but cannot be reasonably explained from known characteristics of the study drug.
Unrelated	An AE that is known, beyond all reasonable doubt, to be caused by a concurrent illness, a concomitant medication, or other means, and not study drug. By definition, AE that occur prior to study drug administration are unrelated to study drug.

6.8.5 *Expected Adverse Events*

Adverse events associated with somavaratan administration have been generally mild and transient and have been similar to those typically observed when rhGH is introduced in GHD patients. The frequency of related adverse events decreased during each successive 6 month

treatment period. During the first 6 months (Phase 1b/2a; Protocol 12VR2), 34 of 64 subjects (53.1%) reported a related AE. In the second 6 months (Protocol 13VR3), 9 of 56 (16.1%) reported a related AE and in the third 6 months (months 12-18 in Protocol 13VR3) 7 of 56 subjects (12.5%) reported a related AE. In GHD children, related adverse events in 68 children exposed to at least one and up to 18 months of continuous repeat dose somavaratan treatment are listed in Table 7.

Table 7 Somavaratan Related Adverse Events in Pediatric GHD (n = 68)

Adverse Event	Subjects Reporting Event (%)
Subjects with at least one related AE	45 (66.2)
Injection site pain	39 (57.4)
Injection site erythema	8 (11.8)
Headache	8 (11.8)
Pain in extremity	5 (7.4)
Arthralgia	5 (7.4)
Injection site discomfort	3 (4.4)
Injection site reaction	2 (2.9)
Injection site anesthesia	1 (1.5)
Injection site hematoma	1 (1.5)
Injection site hemorrhage	1 (1.5)
Hunger	1 (1.5)
Increased appetite	1 (1.5)
Urticaria	1 (1.5)
Rash maculo-papular	1 (1.5)
Dizziness	1 (1.5)
Migraine	1 (1.5)
Presyncope	1 (1.5)
Sleep apnea syndrome	1 (1.5)
Back pain	1 (1.5)
Bone pain	1 (1.5)

Muscle Spasms	1 (1.5)
Musculoskeletal pain	1 (1.5)
Myalgia	1 (1.5)
Increased blood glucose	1 (1.5)
Decreased Free Thyroxine	1 (1.5)

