9.9 Other Analyses

Estimation of PK and PD parameters (e.g., C_{max} , average concentration) will be performed using non-compartmental methods. Post hoc PK/PD models of IGF-I response to somavaratan and rhGH may be evaluated using appropriate methods.

Pubertal development will be described. Findings from 12-lead ECGs will be described.

In addition, the relationship of the presence of ADAs will be explored. The subjects will be classified as ADA negative, transient or persistent based on Shankar et al., and the relationship of this ADA classification with PK, PD and clinical endpoints will be evaluated.³⁰

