3.2 STUDY SCHEDULE

3.2.1 Schedule of Events – Somavaratan (VRS-317) Subjects

Activity/Assessment	Screening	Day 1	Month 1 ¹	Month 3 ¹	Month 6 ¹	Month 9 ¹	Month 12 ²
Informed Consent/Assent ³	X						
Inclusion/Exclusion Criteria	X						
Medical History	X						
Physical Exam	X				X		X
Brief Physical Exam ⁴		X	X	X		X	
Fundoscopy ⁵	X	X	X	X	X	X	X
Pubertal Staging ⁶	X				X		X
Vital Signs ⁷	X	X	X	X	X	X	X
12-lead ECG ⁸	X			X			
Height ⁹ , Weight ¹⁰	X	X	X	X	X	X	X
PK/PD Samples ¹¹	X	X	X	X	X	X	X
GHBP and ALS		X	X		X		X
Antibody Samples ¹²	X		X	X	X	X	X
Adrenal Assessment ¹³	X						
Hematology ¹⁴	X		X		X		X
Chemistry ¹⁵	X		X		X		X
Hemoglobin A1c	X		X		X		X
Free T4, TSH	X		X		X		X
Urinalysis ¹⁶	X		X		X		X
Bone Age ¹⁷	X						X
Adverse Events ¹⁸		X	X	X	X	X	X
Concomitant Medications	X	X	X	X	X	X	X
Somavaratan Dosing ¹⁹		X					

1. For Month 1, 3 and 9, the visits will occur 3 ± 1 days after a somavaratan dose (peak sample collection). For Month 6, the visit will occur 15 ± 1 days after somavaratan dosing (trough sample collection).
2. Should occur after the end of the last dosing interval and approximately 12 months after the Day 1 visit.
3. Informed consent to be completed by duly authorized subject representative. Assent provided by subject, where required.
4. A directed physical exam to address health complaints and to examine injection sites.
5. Ocular fundoscopy through undilated pupil will be conducted by the PI, sub-investigator, or ophthalmologist to detect signs of intracranial hypertension or retinopathy. In sites outside North America, protocol-required fundoscopy will be conducted at screening. At all sites same day is required as clinically indicated if the subject exhibits signs and symptoms of intracranial hypertension (e.g., severe or prolonged headache lasting more than 12 hours or visual disturbances lasting more than 2 hours). Immediate medical attention is required for subjects who develop signs and symptoms of intracranial hypertension.
6. Tanner staging of pubertal hair (boys and girls), breast development (girls) and estimated testicular volume by orchidometer (boys).

7. Includes temperature, respiratory rate, pulse rate and systolic/diastolic blood pressure taken after 5 minutes rest in a sitting position.
8. All subjects will receive 12-lead ECGs (triplicate tracings) at Screening and Month 3.
9. Heights to be measured without shoes in triplicate by stadiometer. Stadiometer should be calibrated just before use. Required precision ≤ 0.2 cm.

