6.13.5 Laboratory Data

Laboratory data will be reported by analyte for each treatment group. There will not be any hypothesis testing. The laboratory results will be presented at each scheduled time point along with the raw change from Baseline for quantitative data. Presence/absence or normal/abnormal results will be summarized as count and percentage. In addition, shift tables summarizing changes from normal to out-of-normal range will be provided.

A listing of all laboratory data, including unscheduled and any follow up evaluations will be provided to supplement the tabulated results.

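### The only planned ECG count leaves out children whose screening ECG was already abnormal, and its denominator is not stated; the laboratory shift tables have a smaller gap of the same kind

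*SAP*

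**What the plan says.** **ECG.** The schedule in SAP 3.2.1 states: "All subjects will receive 12-lead ECGs (triplicate tracings) at Screening and Month 3". Protocol 6.5 places the Month 3 recording at the expected somavaratan peak. Protocol 9.9 says only: "Findings from 12-lead ECGs will be described". SAP 6.13.3 plans two outputs. The first is a listing: "ECG abnormalities from Screening and Month 3 will be listed". The second is "A count and percent of subjects with abnormal changes", and a parenthesis defines what is counted: "subjects with abnormal changes (normal at screening, abnormal findings at Month 3". The denominator is not given. SAP 6.1 has only a general sentence that counts are shown with percentages of subjects in each group.

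**Laboratory.** In SAP 6.13.5, "shift tables summarizing changes from normal to out-of-normal range will be provided". They come on top of results and change from baseline at each scheduled visit, normal/abnormal counts, and a listing of all laboratory data.

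**Adverse events.** SAP 6.13.1 treats a condition present at entry that becomes more severe or more frequent as treatment-emergent. Protocol 6.8 makes a rise in CTCAE grade from baseline an adverse event.

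**The concern.** A child whose screening ECG is abnormal cannot satisfy the 6.13.3 rule, whatever Month 3 shows. Such children can be enrolled: exclusion 12 (Protocol 4.3) concerns screening laboratory studies, and no criterion mentions ECG. The one ECG summary is thus narrower than the SAP's own idea of an emergent event.

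Neighbouring sections are not limited in this way. Physical examinations (6.13.2) are tabulated in three categories at each scheduled visit. Fundoscopy (6.13.4) reports all abnormal results and also sends them to the adverse event summaries. ECG has neither provision.

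Safety comparison is part of the primary objective (SAP 2.1), and there is only one on-treatment ECG. The arm-level figure that a reader will take from the study report should cover every child who had that recording, or say plainly whom it omits.

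The laboratory shift tables, as worded, also have no cell for a value that is abnormal at baseline and worsens, or that moves from low to high.

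**Working it through.** The plan states no ECG or laboratory abnormality rate, so there is no figure to reproduce. The check is a reading of the rule, followed by an illustration with assumed rates.

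**Reading the rule**

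- Normal at screening, abnormal at Month 3: counted.
- Abnormal at screening, with a different or worse abnormality at Month 3: not counted, but listed. It reaches the adverse event tables only if judged an adverse event.
- Abnormal at screening, unchanged at Month 3: not counted, and rightly so.

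The second line is the gap. The adverse event route covers it in part. Protocol 6.8.6 makes laboratory, vital sign and examination findings adverse events when the investigator judges them clinically significant or they otherwise qualify, and it does not name ECG. A new finding that is not judged to be an adverse event would therefore be counted in a child normal at screening but only listed in a child abnormal at screening.

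**Effect of the denominator**

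Assumptions, none from the documents:

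- b = share of children abnormal at screening
- p = rate of new abnormality among those normal at screening
- q = rate of new or worse abnormality among those abnormal at screening

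Three quantities follow:

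- SAP rule over all subjects: (1 − b)p
- SAP rule over those normal at screening: p
- Any new or worse abnormality over all subjects: (1 − b)p + bq

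With an all-subject denominator the shortfall is bq. With p = 5% and q = 20%, at b = 10% the rule gives 0.90 × 5% = 4.5%, against 4.5% + 0.10 × 20% = 6.5%. Over a range of b:

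| b | SAP rule, all subjects | SAP rule, normal at screening | Any new or worse, all subjects |
|---|---|---|---|
| 0% | 5.0% | 5.0% | 5.0% |
| 2% | 4.9% | 5.0% | 5.3% |
| 5% | 4.75% | 5.0% | 5.75% |
| 10% | 4.5% | 5.0% | 6.5% |
| 20% | 4.0% | 5.0% | 8.0% |

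Other assumptions change the picture:

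- **Equal risk (p = q = 10%).** Over all subjects the rule gives 9.0% at b = 10% and 8.0% at b = 20%, against 10.0%. Over those normal at screening it gives 10.0%, with no difference.
- **No new findings in children abnormal at screening (q = 0, p = 5%, b = 10%).** Over all subjects there is no difference (4.5% each). Over those normal at screening, the SAP figure is higher than the all-subject rate (5.0% against 4.5%).

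**Children left out of the count (N × b × q)**

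- At the maximum arm sizes of 102 and 34 (Protocol 4.1), with b = 10% and q = 20%: 102 × 0.02 = 2.04 and 34 × 0.02 = 0.68.
- At the planned 84, split 3:1 as 63 and 21, with b = q = 10%: 63 × 0.01 = 0.63 and 21 × 0.01 = 0.21, or 0.84 of a child in total.

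**The case against.** The strongest reply is that nothing is lost and nothing is mislabelled. The SAP says in parentheses what it counts, and normal-to-abnormal is a recognised definition of an emergent abnormality. Every abnormal ECG is listed, which is workable with at most 136 children and two time points. A clinically important worsening can be reported as an adverse event and tabulated by arm. No formal safety tests are planned (Protocol 9.1). All of this stands, and it keeps the point minor. It does not close the gap: a listing gives no arm-level rate, and the adverse event route depends on judgement.

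Three stronger readings are tempting, and the documents do not support them.

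- **Such findings are never counted.** They are listed, and they enter the adverse event tables when judged adverse events.
- **The reported percentage is too low.** That needs an all-subject denominator and some new or worse findings in children abnormal at entry. The general sentence in SAP 6.1 points towards all subjects but does not settle it for this output. A chance imbalance in screening abnormalities between arms would add little: with an all-subject denominator and p = 10%, a 10-point difference in b moves the reported percentage by 0.10 × 10% = 1 point, while one child among 21 is 1/21 = 4.8 points.
- **Laboratory worsening, free T4 above all, goes unseen.** Inclusion 8 does offer an alternative to normal results: "Normal thyroid function test results at screening visit (or a minimum of four weeks of thyroxine replacement therapy". But exclusions 12 and 16 bar significant screening laboratory abnormalities and improperly treated pituitary deficiencies. Change from baseline, normal/abnormal counts and full listings cover all children. The entry "Decreased Free Thyroxine" in Protocol Table 7 is one child of 68, recorded as an adverse event, so that route can pick up such a finding.

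**Conclusion.** The concern holds in a limited form. The only ECG count and percentage in the SAP omits any child with an abnormal screening ECG who has a new or worse abnormality at Month 3, and its denominator is unstated. If the denominator is all subjects, the percentage understates new or worse findings by bq: from nothing (b = 0 or q = 0) to 4 points at b = 20% and q = 20%, all assumed values. If it is only children normal at screening, the figure is a valid incidence among those at risk and says nothing about the others. The laboratory shift tables have the same gap as worded, but it matters less because other planned outputs cover all children. This is a descriptive safety-reporting weakness of minor severity. It has no bearing on the primary efficacy analysis.

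**What to change.** **SAP 6.13.3.** Present a screening-by-Month 3 ECG shift table by treatment group, using the interpretation categories actually recorded. Take subjects with both ECGs as the denominator and say so. Count as emergent any Month 3 abnormality that was absent at screening, whatever the screening category. The documents do not say how ECG interpretations are recorded. The physical examination grading by clinical significance should therefore not be assumed to apply, and the categories should be checked against the case report form before the table is specified.

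**SAP 6.13.5.** Make the shift tables full: low/normal/high at baseline by low/normal/high after baseline.

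**Cost.** A few lines of SAP wording before database lock and minor programming. No new assessments are needed, provided the recorded ECG findings are detailed enough to tell a new abnormality from an old one. The reported emergent percentage may become slightly less favourable.

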6.13.4 Ocular Fundoscopy

For the fundoscopy examination, the proportion of subjects reporting abnormal results will be calculated and presented by treatment group. Abnormal findings will also be included as AEs for the AE summaries.

A listing of all fundoscopy data will be provided to supplement the tabulated results.

6.13.5 Laboratory Data

Laboratory data will be reported by analyte for each treatment group. There will not be any hypothesis testing. The laboratory results will be presented at each scheduled time point along with the raw change from Baseline for quantitative data. Presence/absence or normal/abnormal results will be summarized as count and percentage. In addition, shift tables summarizing changes from normal to out-of-normal range will be provided.

A listing of all laboratory data, including unscheduled and any follow up evaluations will be provided to supplement the tabulated results.

6.13.6 Medical History

Medical History data will not be tabulated but will be provided in a listing by treatment group and subject.

6.13.7 Concomitant Medications

Concomitant Medications will be coded using the World Health Organization (WHO) Drug dictionary, version as noted in the Data Management Plan, using Anatomical Therapeutic Chemical (ATC) classifications and WHO preferred terms. Concomitant Medications will not be tabulated but will be provided in a listing by treatment group and subject.

8. TABLES, LISTINGS, AND FIGURES

The final list of Tables, Listings, and Figures (TLFs) used in the clinical study report will be provided outside of this SAP prior to database lock.

9. APPENDICES

None.
